4.1 SUBJECT POPULATION

The study population will include subjects with persistent atrial fibrillation (sustained AF episode lasting more than 7 days, but less than 1 year), according to current guideline indications for persistent AF ablation.

Approximately 90 subjects will be enrolled in this study following a 1:1 ratio (intervention: conventional). A total of 4 high-volume sites will be enrolling subjects for this study. Estimated enrollment will be 1-2 subject per study site per month. Patients will be randomized following AF ablation and ICM implant and will be followed for 12 months after a 3 month blanking period.

Gender and Age

Male and female subjects 18 years or older will be. We expect to enroll about 25% women.

Racial and Ethnic Origin

There are no restrictions on race or ethnicity in this study. We expect to enroll about 25% minority subjects.

Inclusion of Vulnerable Populations:

Vulnerable populations: Women of childbearing potential are included if they are currently on the medications to be optimized.

4.2 STUDY INTERVENTIONS

Please see section 8 entitled study procedures that includes further study interventions.

Devices

This study is not studying devices but will utilize data already clinically used and available from the Biotronik ICM. Before or at the time of ablation for persistent AF, all subjects will be implanted with a Biotronik ICM. The Biotronik ICM is FDA approved and will be used per the current FDA indications and is used as standard of care to monitor arrhythmias following AF ablation.

5. INCLUSION AND EXCLUSION CRITERIA

Inclusion criteria

- 18 years of age or older
- History of persistent atrial fibrillation (sustained AF episode lasting more than 7 days, but less than a year)
- Planned to undergo **first** AF ablation with successful Biotronik ICM implant before or at time of ablation

Exclusion criteria

- Paroxysmal atrial fibrillation
- Long persistent atrial fibrillation (continuous atrial fibrillation that lasts more than 1 year)
- Permanent atrial fibrillation
- Left atrial diameter of 60 mm or greater
- Patients with CHF status prohibiting EP study and ablation, but may be re-considered for enrollment later after effective treatment
- Patients with metabolic derangements (e.g. renal/hepatic failure, electrolyte disturbance, etc.), prohibiting EP study and ablation or antiarrhythmic medical therapy (e.g. dofetilide, sotalol or amiodarone, etc.)
- Patients with an intra-cardiac thrombus, but may be re-considered for enrollment later after effective treatment
- Serious known concomitant disease with a life expectancy of < 1 year
- Pregnancy or nursing
- Unwilling or unable to give informed consent
- Existing CIED such as pacemaker or ICD

6. RECRUITMENT METHODS

Subjects will be recruited from ongoing local referrals of patients with persistent atrial fibrillation (sustained AF episode lasting more than 7 days, but less than 1 year), , according to current guideline indications for persistent AF ablation.

Each enrolling site will follow their specific guidelines to determine patient eligibility for this clinical trial. If the patient meets inclusion/exclusion criteria, the study team will approach potential subjects for participation in the study based on the policies of each enrolling site.

7. CONSENT PROCESS

A model consent document as well as the study protocol will be provided to each site to obtain local IRB approval. Revisions to the model consent require approval from the Coordinating Center prior to submission of the consent to the participating site IRB.

The informed consent process will be conducted by the Principal Investigator or individual authorized to conduct the process and will follow the local applicable laws, rules, regulations and guidelines. The consent document will be used as a guide for discussion with the potential subject. The potential subject will be given sufficient time to ask questions and to consider their participation. Refusal to participate or withdrawal from the study will not interfere with future medical treatment. All participants will receive a copy of their signed informed consent and the original will be maintained at the enrolling site. Subject recruitment at an enrolling site may not begin until local IRB-approval is obtained related to the study protocol and consent.

8. STUDY PROCEDURES

After signing the informed consent and undergoing ICM implant prior to or at time of the AF ablation as part of standard of care, subjects will undergo randomization and the following procedures:

12 lead ECG performed as standard of care.

- Quality of life (QOL) questionnaire will be completed by the patients as part of the research study on a paper form and entered into an electronic database by the research coordinator. The questionnaire should take the patient approximately ten minutes to complete.
- Chart Review: Data regarding clinical history, medications, ablation procedure, device implantation, and follow-up data will be collected from electronic medical records prior to in-clinic or follow up calls with the patients.
- In-Clinic Visits: Per standard of care, patients will attend scheduled follow up visits at 3, 9, and 15 months. The study team will perform a medical assessment, and ask questions about adverse events.

- Follow-Up Phone Calls: Patients will receive follow-up calls from the study team at 6 and 12 months. The study team will ask questions about medication changes and any unexpected medical (adverse) events as part of research.

Method of Assigning Subjects to Treatment

Subjects will be randomized 1:1 to conventional AF management vs. ICM-guided AF management following ablation for persistent AF. Randomization will occur electronically using the electronic data collection system, TrialMaster that is available 24/7 to all study personnel.

Follow-up Schedule (See also Figure 1 and Table 1)

Following enrollment and randomization to an intervention arm ICM-based AF management vs. conventional AF management, all subjects will have scheduled follow-up visits (clinic or phone) by the study team at quarterly intervals following randomization. ICM data will be collected electronically at monthly intervals.

All subjects will be followed for a time-period of 15 months.

The following data will be collected at these time-points:

Randomization/Baseline: Baseline clinical characteristics, existing echocardiographic measures, labs, QOL questionnaire, and NYHA class will be recorded.

- *Monthly:*
 - Conventional and Interventional arm
 - Obtain ICM data remotely
- *3-months ±14 days from randomization:*
 - Conventional
 - Office visit for clinical assessment
 - Clinical and adverse events
 - Discontinue AAD after 3 months following the AF ablation procedure per treating physician discretion
 - Interventional arm
 - Office visit for clinical assessment
 - Clinical and adverse events
 - Decision on discontinuation of AAD after 3 months based on AF recurrences between 1-3 months detected by the ICM
- *6-months - 7 days/+21 days from randomization:*
 - Conventional
 - Phone follow up for medications
 - Clinical and adverse events
 - Resumption of AAD or repeat AF ablation based on clinical AF recurrence

- Interventional arm
 - Phone follow up for medications
 - Clinical and adverse events
 - Decision on resuming AAD or repeat AF ablation based on AF recurrences detected by the ICM.
- *9-months - 7 days/+21 days from randomization:*
 - Conventional
 - Office visit for clinical assessment
 - Clinical and adverse events
 - Resumption of AAD, repeat AF ablation, or no change in management based on clinical AF recurrence
 - Interventional arm
 - Office visit for clinical assessment
 - Clinical and adverse events
 - Decision on resume AAD or repeat AF ablation based on AF recurrences detected by the ICM.
- *12-months - 7 days/+21 days from randomization:*
 - Conventional
 - Phone follow up for medications
 - Clinical and adverse events
 - Resumption of AAD or repeat AF ablation based on clinical AF recurrence
 - Interventional arm
 - Phone follow up for medications
 - Clinical and adverse events
 - Decision on resume AAD or repeat AF ablation based on AF recurrences detected by the ICM
- *15-months - 7 days/+21 days from randomization:*
 - Conventional
 - Office visit for clinical assessment
 - Clinical and adverse events
 - Resumption of AAD or repeat AF ablation based on clinical AF recurrence
 - QOL questionnaire
 - Interventional arm
 - Phone follow up for medications
 - Clinical and adverse events
 - Decision on resume AAD or repeat AF ablation based on AF recurrences detected by the ICM
 - QOL questionnaire

Table 1: Data Collection Timepoints

	Screen/ Consent/ Random- ization	FOLLOW-UP					
Timeline		Monthly intervals after randomization	3 calendar months from randomization ± 14 days	6 calendar months from randomization - 7/+21 days	9 calendar months from randomization - 7/+21 days	12 calendar months from randomization - 7/+21 days	15 calendar months from randomization - 7/+21 days
Eligibility Confirmation/ Randomization	✓						
Demographics, PE, Medical Hx/NYHA	✓						
12 lead ECG (SOC)	✓		✓		✓		✓
Echocardiogram (SOC)	✓						
Labs (SOC)	✓						
Vitals (SOC)	✓			✓		✓	✓
CV Medication	✓		✓	✓	✓	✓	✓
Quality of Life	✓						✓
ICM Implant (SOC)	✓						
Ablation Procedure	✓						
In-person Visit (SOC)/Clinical Events			✓		✓		✓
Phone Follow-Up/ Clinical Events				✓		✓	
ICM Remote Monitoring (SOC)		✓					
Adverse Event	✓	✓	✓	✓	✓	✓	✓
Protocol Deviation	✓	✓	✓	✓	✓	✓	✓

Plans for return of research results:

Research results will not be provided directly to patients, but will be presented in national conferences and published in peer-reviewed papers after study completion. If requested by patients, we will send the published research results to patients.

9. RISKS TO SUBJECTS

This is a prospective study in subjects with persistent AF undergoing ablation and ICM implant prior to randomization. The study is not evaluating any medical device. The study includes the use of a currently available ICM to investigate the efficacy of an insertable cardiac monitor-guided atrial fibrillation (AF) management in reducing subsequent atrial arrhythmia burden.

There is some risk associated with the use of any medication. It is important to note that in this study, we are using standard of care and recommended guideline directed medications already indicated in this population of patients; which are often associated with improved outcomes. We are not testing new medications. Medications inherently may be associated with side effects. The clinical research team is experienced in cardiovascular trials and the clinical management of patients with heart disease/heart failure and will be monitoring for any adverse effects and adjust medications accordingly. This is a Phase 4 study, and we are comparing two management strategies that are currently employed in clinical practice.

The risk to participating in this study may include a potential risk of a breach in confidentiality. Every effort will be made to keep the data confidential. To protect against this risk the information collected at each enrolling site will be entered by site personnel into a password protected electronic data capture (EDC) system. Subjects will be assigned a unique subject identification number at the time of registration, which is completed in the EDC system. The subject identification number is not connected with any PHI, such as date of birth or medical record. Each enrolling site will maintain an internal key linking the subject's name with the study data and will not be shared with anyone outside of the enrolling site.

10. POTENTIAL BENEFITS TO SUBJECTS

There are no potential benefits to subjects.

11. COSTS FOR PARTICIPATION

There are no additional costs to the subject. All office visit/procedures follows standard of care guidelines.

12. PAYMENT FOR PARTICIPATION

Subjects will be reimbursed per the institutional policies for each enrolling site (e.g., cash,

check, gift card).

13. SUBJECT WITHDRAWALS

Subjects enrolled in the study may be withdrawn prior to the study completion for a variety of reasons including:

- Subject withdraws consent for any reason;
- Subject is lost to follow up despite best efforts to locate the subject;
- Subject is withdrawn at study investigator discretion.

Subjects may be considered lost to follow up after missing two consecutive follow-up visits with documented efforts to contact the subject.

These subjects will not undergo any additional study activities after withdrawal. If a subject becomes pregnant during the course of a study, they will continue to be monitored but no longer be part of the interventional arm. Data collection will occur until the date of withdrawal and utilized in the study analysis.

Patients who complete fewer than 3 months of follow-up and thus will not complete the blanking period will be excluded from primary end-point analysis, but will be included for all secondary end-points. Withdrawn subjects who have been randomized will not be replaced.

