- Cox proportional hazards regression for risk factors associated with AF recurrence.
- Poisson regression for healthcare utilization.
- Mixed-effects models for QOL changes over time.

Subgroup Analyses:

- Stratification by baseline AF burden, age, and sex.
- Sensitivity analysis excluding early dropout subjects.

7. Data Handling

- All analyses will follow an ITT approach.
- Missing data will be addressed using multiple imputation and sensitivity analyses.
- Data management will be conducted per Good Clinical Practice (GCP) guidelines.

8. Reporting and Interpretation

- All results will be reported with 95% confidence intervals and p-values.
- Statistical significance is defined as $p < 0.05$.
- Study findings will be presented in accordance with CONSORT guidelines.

9. Conclusion This SAP ensures rigorous and transparent statistical analyses for the HYBRID-AF Trial, aligning with ClinicalTrials.gov reporting requirements.

Hybrid Ablation Plus Medical Therapy for Persistent Atrial Fibrillation

Lead Principal Investigator: [name]

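### Protocol Section 13 ends all data collection at withdrawal whatever the reason, although the primary endpoint is read remotely from an implanted monitor and does not depend on visits

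*Combined protocol and SAP*

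**What the plan says.** Protocol Section 13 (Subject Withdrawals) gives three routes out of the study: the subject withdraws consent, the subject is lost to follow-up, or "Subject is withdrawn at study investigator discretion". No criteria are attached to the last. On the second it says "Subjects may be considered lost to follow up after missing two consecutive follow-up visits with documented efforts to contact the subject". The consequences are the same for all three: "These subjects will not undergo any additional study activities after withdrawal" and "Data collection will occur until the date of withdrawal and utilized in the study analysis". The same section adds that "Patients who complete fewer than 3 months of follow-up and thus will not complete the blanking period will be excluded from primary end-point analysis".

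The primary endpoint has a different source from the visits. SAP Section 4 defines it as the share of time in AF between months 3 and 15 after ablation, as measured by the ICM. Protocol Section 4.2 has every subject implanted and calls the device standard of care. Protocol Section 8 says "ICM data will be collected electronically at monthly intervals", remotely and in both arms, and Table 1 lists this as a monthly standard-of-care item, separate from the clinic visits (months 3, 9, 15) and phone calls (months 6, 12). Follow-up data are also taken from chart review.

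For analysis, SAP Section 7 says "All analyses will follow an ITT approach" and plans multiple imputation with sensitivity analyses for missing data. Nothing elsewhere in either document keeps ICM collection going for a subject who leaves without withdrawing consent.

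**The concern.** Stopping attendance, stopping the assigned strategy and refusing further use of data are different events, and only the last obliges the trial to stop collecting. Section 13 treats them as one. Because Section 8 counts phone contacts as follow-up visits, one missed clinic visit followed by one missed call is enough to make a subject eligible to be declared lost, while the implanted monitor may still be recording the primary endpoint.

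Two things are at stake. The first is information: months of the primary window that could have been observed become missing and are then imputed or left out of the subject's percentage. The second is possible bias. Treating physicians know which strategy the patient is assigned to, and in the intervention arm they receive monthly AF reports, so leaving the study could be related to arm and to AF status. An observed value is better than an imputed one in that situation, because the imputation model cannot check its own assumptions.

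**Working it through.** **Inputs.** Total 90 subjects, 1:1, two-sided alpha 0.05, power 80%, burden 25% against 16% (difference 9 points), SD 15 points, drop-out 10% (SAP Section 5; protocol Section 17). Primary window: months 3 to 15, that is 12 months. Contacts at months 3, 6, 9, 12 and 15. Loss may be declared after two consecutive missed contacts.

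**1. The plan's own sample size.** Per arm, n = 2 × [SD × (1.960 + 0.842) / difference]² = 2 × [15 × 2.802 / 9]² = 43.6, so 44 per arm and 88 in total. Inflating for 10% drop-out gives 88 / 0.90 = 97.8, or 98. The stated 90 is therefore matched before inflation but not after it, unless the remark in Section 17 that the SD already allows for drop-out is meant to cover it. For this point it matters only that there is little spare power.

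**2. Window lost per subject.** Take the withdrawal date as the second missed contact:

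- months 3 and 6 missed: 15 − 6 = 9 of 12 months lost (75%)
- months 6 and 9 missed: 15 − 9 = 6 of 12 (50%)
- months 9 and 12 missed: 15 − 12 = 3 of 12 (25%)
- months 12 and 15 missed: about none

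The visit windows make these dates approximate.

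**3. Upper bound on endpoint time lost.** The plan's 10% drop-out is 0.10 × 90 = 9 subjects. Planned endpoint time is 90 × 12 = 1,080 subject-months. If all 9 left by a route other than consent withdrawal:

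- at month 6: 9 × 9 = 81 months, 81 / 1,080 = 7.5%
- at month 9: 9 × 6 = 54 months, 5%
- at month 12: 9 × 3 = 27 months, 2.5%

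**4. Upper bound on power lost.** Suppose instead that all 9 gave no usable primary value, leaving 81 subjects (40.5 per arm). With power = Φ[9 / (15 × √(2/m)) − 1.960]:

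- m = 45: Φ(2.846 − 1.960) = Φ(0.886) = 81.2%
- m = 40.5: Φ(2.700 − 1.960) = Φ(0.740) = 77.0%

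Applying the rank-sum test's relative efficiency of 3/π for normal data gives 79.4% and 75.1%. Either way the loss is about 4 percentage points.

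**5. When step 4 could apply.** A subject lost at month 6 or later has at least three months of window data. Section 13 says data up to withdrawal are used, and protocol Section 17 expresses burden as a percentage of follow-up, so that subject still has a value. Total loss through missed visits needs the withdrawal date to be set back to a last contact before month 3, which would bring in the under-3-months exclusion. The documents do not define the date for a lost subject.

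**The case against.** The strongest reply is that the rule is milder in practice than a bare reading suggests. Loss to follow-up requires best efforts to find the subject, two missed contacts in a row and a record of the attempts, and even then it is discretionary. Data up to withdrawal are kept, and imputation and sensitivity analyses are planned. This stands, and it is why the figures above are bounds. It does not remove the point, because once a subject is declared lost or withdrawn, no provision lets collection continue.

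Some stronger readings are tempting, but the documents do not support them:

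- A reader might infer that all 9 planned drop-outs are affected. The 10% is total drop-out. It is not split by reason and includes consent withdrawals, for which stopping is proper.
- A reader might try to state the bias in points of AF burden. That needs an assumed gap between lost and retained subjects and an assumed imbalance between arms, and neither is in the documents. A shift in means would also not map directly onto a rank-sum test.
- A reader might infer from the pregnancy sentence, "they will continue to be monitored but no longer be part of the interventional arm", that a randomised subject is removed from her arm in the analysis. The sentence keeps her monitored and states no analysis reassignment, and the SAP specifies ITT. It can be read simply as ending the assigned management.
- A reader might see the stop rule itself as a breach of ITT. It creates missing data but reassigns and excludes nobody. The under-3-months exclusion is a separate matter.
- A reader might assume that the lost data were free for the taking. That the device goes on transmitting is an inference from its being implanted and remotely monitored. All interrogations go to an adjudication committee (protocol Section 4), and use depends on consent terms that are not in the public text.

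**Conclusion.** The point holds as a cheap improvement to the plan. Followed as written, Section 13 discards primary data that could probably be obtained from subjects who have not withdrawn consent. The cost is 9, 6 or 3 of 12 window months for a subject declared lost at month 6, 9 or 12. Over the whole trial it is at most 7.5%, 5% or 2.5% of endpoint time, and about 4 points of power (81% to 77%) in the extreme case where all 9 drop-outs have no usable value. These bounds assume that every planned drop-out leaves by a route other than consent withdrawal and that the monitor would otherwise have supplied the data. The actual loss is likely to be smaller.

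The loss may be informative, because assignment is known to those who manage the patient and who may withdraw the subject. Neither the size nor the direction of any resulting bias can be derived from the documents.

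**What to change.** In Section 13 and the SAP, separate two cases:

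- (a) Withdrawal of consent to data use: collection stops at that date.
- (b) Loss to follow-up, refusal of visits or calls, and withdrawal at the investigator's discretion: monthly remote ICM data, and chart-review capture of death, hospitalisation and repeat ablation, continue to month 15, and the subject is analysed in the randomised arm.

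Because the SAP says the trial has concluded, the practical steps are to:

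- retrieve stored ICM transmissions for type (b) subjects where consent allows;
- state how the withdrawal date was set for subjects declared lost;
- report withdrawals by reason and arm;
- use multiple imputation only for what is still missing.

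The cost is some retrieval and adjudication work, limited to what each subject's consent permits. No visits or procedures are added, and the sample size of 90 does not change.

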14. PRIVACY AND CONFIDENTIALITY OF SUBJECTS AND RESEARCH DATA

Data collected during this study will be obtained for research purposes and derived from study procedures, study ICM device, subject records and subject visits. All study data will be stored in a password-protected database located at the CCRC per Section 15 and de-identified. To protect confidentiality and privacy, subject data will be assigned a code using a unique subject ID number at the time of randomization and linked to subject identifiers that are stored separately in a study log solely maintained by the enrolling site study coordinator. The electronic data will be directly entered and extracted from computer system for data collection using encryption and physical controls. There is no plan to share, transmit or transfer the data.

